6.1 Study center

This study will be conducted in properly equipped and registered ophthalmology offices. Depending on the sponsor's needs, these offices may be private or public, attached to a hospital or clinic, or independent.

6.1.1 Organization of the center

Each study center will have a principal investigator (PI). The PI is the ophthalmology specialist leading the clinical study.

The PI is responsible for forming a multidisciplinary research team to execute the clinical study according to the protocol, under his or her scientific guidance. The PI is responsible for designing the organization of his or her center and selecting the personnel who will perform these functions. However, the minimum organization of the research team requested by the sponsor requires the following: a sub-investigator , study coordinator, and pharmacist. (See **Figure 2Minimum organization of the center.**)

Any person designated by the PI as responsible for monitoring the study (coinvestigator, sub-investigator, nurse, etc.) or for a specific role in the study (pharmacist, administrative assistant, study coordinator, etc.) must be listed on the “Delegation of Responsibilities” form.

[figure not shown]

Figure 2Minimum organization of the center

The "Delegation of Responsibilities" and the "Center Organizational Chart" must be submitted to the sponsor before the start of the study and updated if the members or their responsibilities change.

6.1.2 Documentation to be delivered to the sponsor

The IP must submit to the sponsor, before the start of the study:

- Updated *curriculum vitae* , in Spanish, dated and signed (maximum 10 pages), of the IP and the staff that make up the center's organizational chart.
- Copy of academic certifications from the IP (degree and specialty diploma in ophthalmology; federal professional licenses)
- A copy of academic certifications of the highest degree obtained by each member of your research team, which support their ability to perform the delegated functions.

- Copy of the notice of operation or similar issued by the corresponding regulatory entity (when applicable)
- A valid certificate of good clinical practice. If the issuing institution does not specify the validity period in the certificate, the certificate issue date must not be more than one year old.

6.1.3 Closure of the center

The closure of the center will be agreed upon in advance by the sponsor and the PI, once the last visit of the last enrolled subject has been completed. The closure process will be in accordance with the sponsor's internal operating procedures.

It is the sponsor's prerogative to close a study center prematurely; they must inform the IP of the reasons for the closure.

6.2 Eligibility criteria

6.2.1 Inclusion criteria

- Signed informed consent.
- Systemically and ophthalmologically healthy subjects evaluated during the medical history.
- Age between 18 and 45 years.
- Both sexes.
- Blood tests [complete blood count (CBC), three-element blood chemistry (BC), and liver function tests (LFTs)] within normal parameters specified by the reference laboratory with a lower and upper margin of 10%.
- Vital signs are within normal limits. (Resting vital signs: blood pressure \leq 139/89 mmHg , heart rate 60-100 beats per minute, and respiratory rate 12-24 breaths per minute)
- Visual capacity 20/30 or better, in both eyes.
- Intraocular pressure \geq 11 and \leq 21 mmHg .

6.2.2 Exclusion criteria

6.2.2.1 General criteria

- Subjects with a history of hypersensitivity to any of the components of the investigational products.
- Subjects who are users of topical ophthalmic medications of any pharmacological group.
- Subjects who use medications by any other route of administration.
- Pregnant or breastfeeding women.
- Women with no history of bilateral tubal obstruction , oophorectomy or hysterectomy, who do not ensure a hormonal contraceptive method or intrauterine device during the study period.
- Subjects with participation in clinical research studies 90 days prior to inclusion in this study.
- Known diagnosis of liver disease
- Inability to attend or respond to assessments conducted at each visit.
- Positive smoking (specified as cigarette consumption regardless of quantity and frequency)
- Positive alcoholism (specified as the consumption of alcoholic beverages, regardless of quantity and frequency, during the study intervention period).
- Contact lens wearers.

6.2.2.2 Medical and therapeutic criteria

- History of any chronic-degenerative disease.
- Inflammatory or infectious disease, active at the time of entering the study.

- Unresolved injuries or trauma at the time of study entry.

6.2.3 Elimination criteria

- Withdrawal of the consent letter under information.
- Presentation of a serious adverse event.
- Non-tolerability or hypersensitivity to any of the compounds used during the tests (fluorescein, lissamine green , tetracaine)
- Non-tolerability or hypersensitivity to any of the investigational drugs.
- Adherence < 50% determined by subject's diary.

6.2.4 Subject identification

Patients in the study will be identified by a number and their initials.

The initials of the subject of study will be obtained starting with the first letter of the name, followed by the first letter of the first surname and the first letter of the second surname, obtaining a maximum of three letters. In case the person has two names or a compound surname, the first letter will always be used.

[figure not shown]
Example:

1. [name]
 - a. Initials: AMC
2. [name]
 - a. Initials: JDO

During the screening phase, participants will be assigned a consecutive three-digit number. Once the subject has been selected, they will be assigned a number that will identify them throughout the study. This code will consist of eight numbers in the following order, from left to right:

- three digits of the molecule under study according to the name given by the sponsor.
- two digits corresponding to the research center number.
- three digits of the consecutive number assigned to its inclusion in the research center.

Example:

6.3 Intervention

6.3.1 Treatments administered

6.3.1.1 Treatment under study

- **PRO-165**
 - Active ingredients (lubricant): sodium hyaluronate 0.2%
 - Pharmaceutical form: Ophthalmic gel
 - Prepared by: Laboratorios Sophia , SA de CV
 - Dosage: One drop of gel, 4 times a day during the waking period, in the fornix of the right eye.

- Formulation description: Clear gel, free of visible particles.
- Packaging description: Sterile multi-dose tube, low-density polyethylene and aluminum polylaminate with high-density polyethylene cap.

Table 4Qualitative -quantitative formulation of PRO -165

Agent type	Amount mg/ mL	Function
Sodium hyaluronate	2.0	Active ingredient
Chondroitin sulfate	Not shown	Viscosant
Polyoxylated Castor Oil 35	Not shown	Solubilizer
Polyethylene glycol 8000¹	Not shown	Cosolvent
Eddate disodium dihydrate	Not shown	Chelating agent
Cetrimide	Not shown	Conservative
Glycerin	Not shown	Osmoregulator
Sodium hydroxide	Not shown	pH adjustment
Homopolymer carbomer type B²	Not shown	Gelling agent
Polycarbophil³	Not shown	Gelling agent
Water for the preparation of injectables cbp⁴	Not shown	Vehicle

Qualitative and quantitative formulation of the investigational product PRO-165. The concentration of the active ingredient is shown, as well as the substances that act as additives. (1) Synonym of Carbowax® (2) Synonym of Carbopol® 974P NF Polymer, USP (3) Synonym of Noveon® AA-1 Polycarbofil, USP (4) as much as is sufficient for

6.3.1.2 Reference treatment

- **Artelac® Nightime Gel**
- Active ingredients: Carbomer 0.2%
- Pharmaceutical form: Ophthalmic gel
- Prepared by: [name] Chem Pharm. Fabrik GmbH [name] . Imported and marketed by: Bausch & Lomb México, SA de CV, [name].
- Dosage : One drop of gel, 4 times a day during the waking period, in the fornix of the right eye.
- Solution description: Clear gel, free of visible particles.
- Packaging description: Sterile multi-dose tube.
- Characterization: The characterization, stability, and formulation of the comparator will be supported by its packaging, lot number, and IPP, a copy of which will be kept in the study's master folder.

6.3.2 Strategies to improve adherence and procedure to monitor adherence

Adherence to the intervention is essential to achieve the objectives of clinical research. Adherence is defined as: "the extent to which people's behavior (including medication intake) corresponds to

the instructions of the health service provider." [33]The safety profile of a product may be under- or overvalued due to poor adherence.

The strategies to be carried out to improve adherence are:

1. Direct questioning by the IP regarding the application of the intervention.
2. At the IP's discretion, reminder messages or calls may be sent.
3. Delivery of a printed schedule specifying the date of the visit and its activities
4. Subject's diary.

6.3.2.1 Procedure for monitoring adherence

For more than four decades, numerous studies have been conducted on the appropriate way to measure and quantify medication adherence, but none have reached a consensus that could serve as the gold standard, whether in cross-sectional or longitudinal studies. [34] [35] [36] [37] [38] [39] [40] [41]

There are different procedures for measuring adherence to pharmacological interventions. The most common procedure involves self-reports , which include patient interviews, questionnaires, and self-monitoring diaries. Their strengths are speed, flexibility, low cost, and ease of implementation; they have a high degree of specificity for non-adherence, but their sensitivity and reliability for adherence are low. [41] [42]

Biochemical measurement of the drug, or its metabolite, is one of the methods that best confirms drug use. However, in addition to being costly and impractical, it is of little use in ophthalmic applications, as peripheral concentrations may be undetectable; and samples from other tissues require more invasive methods that would be inadvisable. [41]

Medication counting is another way to measure adherence. Classically referred to as "pill counting," in ophthalmology it is translated as the weight of the bottle. This is a simple, inexpensive, and noninvasive method. The main disadvantages of this method are: 1. It cannot confirm medication application (it could have been intentionally dropped or instilled outside the eye), and 2. It depends on the subject bringing the medication back. [41] [42]

A multi-method approach to adherence measurement is recommended. Because there is no ideal adherence measure, it is appropriate to use more than one method when aiming to achieve results that resemble reality. Selecting two or more methods allows for balancing their strengths and weaknesses, thus more accurately capturing adherence levels. [40]

Adherence assessment will be facilitated by the subject's diary and will be performed as follows:

$$Ad = (A_r)100/A_i$$

Ad= Adhesion

A_r= Registered applications

A_i= Applications indicated for the intervention

Final adherence will be determined by the average adherence from each visit. Overall adherence (all subjects) will be determined by the average of each subject's final adherence.

Adherence to the procedure, taking into account weight, will be calculated as follows: the weight of the empty tube, the weight of the drop, the weight of the tube with its contents, the total amount of gel to be applied during the entire procedure, and the total weight of the gel applied. The following simplified formula will be used:

$$Ad = \frac{(P_i - P_f)100}{P_T}$$

Where:

Ad = adhesion

P_i = weight of the tube delivered to the subject at the start

P_f = weight of the tube returned by the subject

P_T = weight of the dosage indicated for the intervention

$$P_T = (P_g)G$$

Where:

P_g = weight of a drop of the intervention, determined by the research and development department

G = number of applications indicated for the intervention

It will not be considered for the calculation of adhesion if the tube does not maintain its physical integrity.

There is no standardized parameter to define adequate adherence; it must be defined and outlined by the objectives of the particular research. [41]

Calculating adhesion by weight is not chosen as the ideal way to monitor adhesion, due to the difficulty in standardizing the amount of product per application, due to the characteristics of the formulation (gel).

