Creation date: february 2017

Phase I clinical study to evaluate the safety and tolerability of PRO-165 ophthalmic gel versus Artelac® Nightime Gel on the ocular surface of ophthalmologically and clinically healthy subjects

Protocol code:SOPH165-0217/I

Protocol version:4.0

Version date: 21/Jan/2022

Clinical Trial ID: NCT04704531

Sponsor: Laboratorios Sophia, S.A. de C.V.

1. Summary

Title of the study:	
Estudio clínico fase I, para evaluar la seguridad y tolerabilidad del gel oftálmico PRO-165 versus Artelac® Nightime Gel, en la superficie ocular de sujetos oftalmológicamente y clínicamente sanos.	
Protocol code: SOPH165-0217/I	Creation date: February 7, 2017
Protocol version: 4.0	Version date: January 21, 2022
Therapeutic indication: Eye lubricant	
Study period: 4 months	Development phase: I
Aim: To evaluate the safety and tolerability of the PRO-165 formulation on the ocular surface of ophthalmologically and clinically healthy subjects.	
Hypothesis: PRO-165 ophthalmic gel presents a safety and tolerability profile similar to Artelac® Nightime Gel in ophthalmologically and clinically healthy subjects.	
Methodology: Phase I, controlled, parallel-group, double-blind, randomized, exploratory clinical study.	
Number of patients: 32 subjects, divided into 2 groups [16 subjects (16 eyes) exposed per group]	
Diagnosis and main inclusion criteria: 
 - Systemically and ophthalmologically healthy subjects - Signed informed consent. - Age between 18 and 45 years. - Both sexes - Blood tests [complete blood count (CBC), three-element blood chemistry (BC), and liver function tests (LFTs)] within normal parameters - Visual capacity 20/30 or better 	
Test product, dose and route of administration, 
 - PRO-165 Sodium hyaluronate 0.2% ophthalmic gel. Manufactured by Laboratorios Sophia , SA de CV, Zapopan, Jalisco, Mexico. 
 ▪ Dosage: One drop of gel, 4 times a day during the waking period, in the fornix of the right eye. 	

▪ Route of administration: ophthalmic
Treatment duration: 10 days
Reference product, dosage and route of administration:

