6.4.4 Time of measurements

Measurements of the primary and secondary outcome variables will be performed and evaluated for each visit, according to the following:

Baseline Visit / Day 0.

Some of these measurements will be performed at the screening visit to complete the eligibility criteria (see Study schedule and diagram), at the discretion of the PI, and if no more than 10 days have passed, they may be taken to complete the baseline visit data.

1. Visual capacity.
2. Intraocular pressure.
3. Eye comfort index
4. Ocular surface evaluation
 - a. Includes stains
 - b. TRL
5. Adverse event evaluation.
6. Vital signs.
7. Evaluation of laboratory test results

Visit 1 / Day 5.

It can be done in a period of \pm 2 days in relation to day 5 of application.

1. Visual capacity.
2. Intraocular pressure.
3. Ocular surface evaluation
 - a. Includes stains
 - b. TRL
4. Vital signs.
5. Adverse event evaluation.

Final Visit / Day 11.

It can be done in a period + 1 day in relation to the 11th day of the start of application, not before the 11th day since the 10 days of application would not be met.

1. Visual capacity.
2. Intraocular pressure.
3. Eye comfort index
4. Ocular surface evaluation
 - a. Includes stains
 - b. TRL
5. Vital signs.
6. Evaluation of adverse events.

Safety Call / Day 13.

It can be carried out within a period of \pm 1 day in relation to the 13th day from the start of application.

1. Ask about the presence of any adverse events.
2. Evaluation of laboratory test results

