For adverse event reporting, all eyes of participants randomized to an intervention group after the baseline visit will be considered. Results will be expressed as the number of cases (eyes).

The final results report will be displayed in tables or graphs, as appropriate.

The investigational drug will be considered safe and tolerable when there are no clinical or statistical differences in all primary outcome variables compared to its comparators.

Subjects with an adherence rate greater than 60% will be included in the statistical analysis to meet the study objective, based on the subject's diary. However, even if the subject's diary indicates adherence greater than 60%, if the adherence calculated by weight is less than 30%, the subject will not be included. The minimum dose necessary to obtain a pharmacological effect (lubricant/1 gel application per day) and the presence of adverse events (exposure) were considered sufficient to meet the overall design objective, in accordance with the pharmacological characteristics of the investigational product.

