- Intra-group difference: McNemar test. This is applied to 2x2 contingency tables with a dichotomous feature, with pairs of paired subjects, to determine if the marginal frequencies of row and column are equal (marginal homogeneity).
- Difference between groups: Pearson's Chi-square (χ^2) test or Fisher's exact test at expected values less than 5.

The level of difference to consider significance (p) will be an alpha (α) of 0.05 or less.

Chondroitin Sulfate 0.18%/Sodium Hyaluronate 0.2%

For the reporting of adverse events, all eyes of those participants who were randomly assigned to an intervention group after PI instillation (ITT) will be considered.

The final report of the results will be shown in tables or graphs, as appropriate.

Those subjects who meet a minimum adherence of 60% will be included in the statistical analysis to meet the objective of the study, taken from the subject's diary. However, even if the subject's adherence is greater than 60% per diary, if the adherence calculated by weight is less than 30%, the subject will not be included.

The investigational drug will be considered safe and tolerable when there are no clinical and statistical differences in all primary outcome variables, with respect to its comparator (Artelac® Nighttime Gel).

Table 3. Triangulation of concepts

Variable Type	Variable	A1	B1	B2	C1	D1	E1	E2	E3	E4	E5	E6	E7	E8
Background														
A1	Demographic			DT										
Basal														
B1	Medical History		DT			T								
B2	Comprehensive ophthalmological evaluation		DT	DT		TB			TB		B	B		T
Safety														
C1	Incidence of AD			TB	TB		TB	TB	TB		TB	TB	TB	TB
Tolerability														
D1	ICO			DB			DB							
Secondary outcome														
E1	TRL			DB		TB		DB						
E2	Vitals			DB		TB			B					

Chondroitin Sulfate 0.18%/Sodium Hyaluronate 0.2%

E3	Posterior segment	DB	TB	B
E4	Quality Questionnaire			TB
E5	PIO	DB	TB	B
E6	Visual Ability	DB	TB	B
E7	Laboratory tests	DB	TB	B
E8	Ocular surface stains	TB	TB	TB

D. Descriptive Statistics; T, 2x2 contingency table; B, Bivariate Analysis; M, Multivariate Analysis.

Changes

1. First version of the document, no changes apply.

Author of the document

Ph.D. in Cs. [name].

Biostatistics.

Clinical Operations.

Laboratorios Sophia, S.A. de C.V.

[name]

[name]

References

<https://doi.org/10.1007/BF03163747>.

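### Final adherence averages two visit percentages with equal weight although the intervals can hold unequal numbers of applications, so the 50% and 60% diary cut-offs depend partly on the date of Visit 1

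*Protocol*

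**What the plan says.** Protocol 6.3.2.1 defines diary adherence as registered applications times 100 over indicated applications, with "A_i= Applications indicated for the intervention". It then combines the visits: "Final adherence will be determined by the average adherence from each visit". No weights are given. The SAP offers no other way to combine visits.

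The schedule in Protocol 6.5 places adherence assessment at Visit 1 and the Final Visit only, so two percentages are averaged. Protocol 6.4.4 allows Visit 1 two days either side "in relation to day 5 of application".

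The diary figure then serves as a filter in three places:

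- Protocol 6.2.3 lists among the elimination criteria "Adherence < 50% determined by subject's diary".
- Protocol 8.3.1: "Subjects with an adherence rate greater than 60% will be included in the statistical analysis to meet the study objective".
- SAP, Methods of Analysis: "Those subjects who meet a minimum adherence of 60% will be included in the statistical analysis".

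The weight-based formula, also in 6.3.2.1, divides by the weight of all indicated applications, so it is already a whole-course figure.

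**The concern.** An average of two percentages equals the overall percentage only if both have the same denominator or the two percentages are equal. Here the denominators depend on a visit date that may move by four days. A short first interval counts as much as a long second one, so a few early applications can dominate the score.

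The score decides who is eliminated and who is analysed. Two subjects with identical diaries can be classified differently only because Visit 1 was held on different permitted days. With 16 subjects per group, moving one or two across a cut-off could visibly affect the comparison of the comfort index, the primary tolerability outcome.

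**Working it through.** The documents give no numerical adherence result, so there is no figure to reproduce. The check compares the stated rule with the pooled proportion.

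**Inputs**
- Dose frequency: "One drop of gel, 4 times a day during the waking period, in the fornix of the right eye" (Protocol 6.3.1.1; the reference arm is the same in 6.3.1.2).
- "Treatment duration: 10 days" (Protocol summary), giving 4 × 10 = 40 applications.
- First application: the day after baseline, i.e. day 1 (Protocol 6.5).
- Visit 1: days 3 to 7. The documents do not say which interval the visit day belongs to. Counting completed days only, the first interval has 2 to 6 days (8 to 24 applications). Counting the visit day, it has 3 to 7 days (12 to 28 applications).

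**Formulas.** Let a and b be the adherence proportions in the two intervals, and w the share of the 40 applications due in the first.
- As written: (a + b)/2
- Pooled: w·a + (1 − w)·b
- Difference: (0.5 − w)(a − b), at most |0.5 − w| in size

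**Bounds, enumerating every pair of counts**

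| Split | Largest gap (points) | Lowest pooled value passing >60% as written | Highest pooled value failing it |
|---|---|---|---|
| 8/32 | 30 | 37.5% | 82.5% |
| 12/28 or 28/12 | 20 | 45.0% | 75.0% |
| 16/24 or 24/16 | 10 | 52.5% | 67.5% |
| 20/20 | 0 | none | none |

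At the 50% cut-off, the same three unequal splits can keep a subject with pooled adherence as low as 20%, 30% or 40%, or eliminate one with pooled adherence as high as 77.5%, 67.5% or 57.5%.

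**Examples**
- 8/8 then 9/32: (100 + 28.1)/2 = 64.1% as written; 17/40 = 42.5% pooled. Analysed, although the pooled value is below the elimination cut-off.
- 2/8 then 29/32: (25 + 90.6)/2 = 57.8%; 31/40 = 77.5%. Not analysed.
- 16/16 then 6/24 (Visit 1 on day 5, completed days only): (100 + 25)/2 = 62.5%; 22/40 = 55.0%. Analysed.

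**One diary, different visit days.** Take four applications a day on days 1–4 and one a day on days 5–10: 22/40 = 55.0% pooled. Counting completed days only:
- Visit 1 on day 3: (8/8 + 14/32)/2 = 71.9%
- Visit 1 on day 5: (16/16 + 6/24)/2 = 62.5%
- Visit 1 on day 7: (18/24 + 4/16)/2 = 50.0%

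This subject is analysed in the first two cases and not in the third.

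**How often.** The documents give no adherence distribution, so this is a range under assumptions. Adherence in the two intervals is taken as independent and beta-distributed. The table gives the share of subjects on whom the two rules disagree at 60%.

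| Mean (SD) | 16/24 split | 8/32 split |
|---|---|---|
| 90% (10%) | 0.1% | 0.6% |
| 80% (15%) | 1.9% | 6.0% |
| 70% (20%) | 5.7% | 14.6% |

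Multiplied by 32 subjects, these are well under one subject, about 0.6 to 1.9, and about 1.8 to 4.7. Adding binomial variation in the counts within each interval raises the three ranges to 0.4–1.5%, 2.9–8.7% and 6.5–17.1%.

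**Alternative reading of A_i.** If A_i meant all 40 applications at each visit, a perfectly adherent subject would score (16/40 + 24/40)/2 = 50%, and nobody could pass 60%. A_i must therefore mean applications due in the interval, which the text should say.

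**The case against.** The strongest reply is that the harm is narrow.

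- A reader might infer that both primary outcomes are filtered by this figure. The text does not support that. Protocol 8.3.1 and the SAP report adverse events on all randomised eyes (the SAP adds after instillation), so the exposed analyses are mainly the comfort index and the secondary variables. This stands.
- A reader might infer that subjects with inadequate exposure are analysed. By the protocol's own standard that does not follow: 8.3.1 treats one application a day as the minimum for effect, about 10 over the course. The fewest recorded applications that still pass 60% as written are 15 (8/32), 18 (12/28) and 21 (16/24). A separate 30% weight criterion, on a whole-course basis, is a further check, although 6.3.2.1 admits that weight is imprecise for a gel. The fault is misclassification against the plan's own cut-offs, not shown under-exposure.
- A reader might expect a large share misclassified. Assuming uniform adherence from 30% to 100% gives about 20% with Visit 1 on day 3 and about 8% on day 5 or 7, but that centres the population at 65%, next to the cut-off. Nothing in the documents supports it. These are healthy volunteers with a diary and direct questioning over 10 days. Correlation within a subject also helps: at mean 80% (SD 15%), a correlation of 0.7 lowers the 8/32 rate from 5.9% to 3.5% and the 16/24 rate from 2.0% to 1.2%.
- Equal weighting is the plain reading of an average, not a stated word, and 6.2.3 and 8.3.1 do not use the term final adherence. Day 3 is the edge of the window. If Visit 1 is on day 5 with that day counted, or on day 6 counting completed days, the split is 20/20 and there is no error.

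These points limit the size. They do not remove the fault: no other way of combining visits is given, and most permitted visit days give unequal intervals.

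**Conclusion.** Wrong as written; low to moderate severity. On its plain reading, the averaging rule does not measure the proportion of indicated applications recorded. The gap can reach 30 points at an 8/32 split and 10 points at 16/24, and is nil at 20/20. These bounds are exact, given 40 applications and two assessments. Classification at 50% and 60% therefore depends partly on the day of Visit 1.

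The expected effect is modest. It needs adherence that differs between intervals and an overall level near a cut-off. Under the independent-beta assumption it runs from under 1% of subjects (mean 90%) through about 2–6% (80%) to about 6–15% (70%), somewhat higher with binomial variation in the counts. No figure in the documents settles which applies.

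The difference between the 50% and 60% cut-offs, and between the protocol's strict and the SAP's inclusive 60%, are separate inconsistencies.

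**What to change.** In Protocol 6.3.2.1, replace the averaging sentence with:

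final adherence = 100 × (sum of registered applications over all diary intervals) / (sum of applications indicated over those same intervals)

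The denominator is 40 for subjects who complete the course. For early stoppers it is the number of applications indicated up to the recorded stop of treatment. It should not be fixed at 40 for everyone: a subject who stops at Visit 1 after 16/16 would then score 16/40 = 40% and fall below both cut-offs, although Protocol 8.3.3 includes anyone who completed Visit 1. With the matched denominator the score is 16/16 = 100%.

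Define A_i as applications indicated in the interval. State that this pooled figure is the one used wherever a diary cut-off is applied (Protocol 6.2.3 and 8.3.1, SAP Methods of Analysis). It then shares the whole-course basis of the weight formula for completers, and for subjects who complete the course it no longer matters which interval the visit day belongs to.

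The cost is one formula and one definition in the protocol, and a matching line in the SAP. The diaries already hold the counts, and no visit, dose or procedure changes.
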